## **2.e Risks and Benefits**

### *Minimization of Risks and Confidentiality*

We are a HIPPA covered entity and comply with all HIPPA regulations. To protect against and minimize potential risks, participants will be carefully screened and evaluated for eligibility by research coordinator. Participants may have the risks of feeling tired or disrupted by home visits, sore muscles after practicing exercise activities, feeling worn out, or confidential information of participants may be accidentally disclosed. Participants may take a break at any time during participation and will be instructed to notify the rater or interventionist if they experience any discomfort.

An ID number will be assigned to each participant. All data collected from a participant will be labeled with the ID number. All participant electronic and hard-copy data will be kept under double-lock protection. All hard copy forms that contain personal identifiers (e.g., name, address, phone numbers) will be stored in a separate locked file drawer under double-lock protection. No publication or presentation of the study data will uniquely identify or provide sufficient information to uniquely identify participants.

To guard against unauthorized data access, all shared-use computer systems at the Washington University School of Medicine are protected with passwords, which are changed at 4-month intervals. Only individuals with a particular "need to know" status are given access, and system privileges are carefully restricted. All personal computers to be used in the Administrative Unit are located within a secure area, and the system is locked when not in use. SAS and SPSS software packages will be used for data management and analysis. Datasets generated from these programs will be password protected, which will make accessing study data difficult even in the event of unauthorized computer access occurs.

There is no proven benefit from being in this study. However, benefits to the participants enrolled in the proposed study are free in-home exercise sessions provide by OT interventionists. Participants in treatment group (Adapted LiFE) may be able to improve balance and muscle strength, and participants in the control group may be able to improve flexibility.

## **2.f When and How to Withdraw Subjects**

Participants will be told that their involvement in this research study is voluntary and that they may choose not to participate or withdraw their consent at any time. There will be no penalty or loss of benefits to which participants are otherwise entitled. Participants

---

will be withdrawn if there is a serious adverse event (SAE) that may impact participant's safety (see F5).

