## **C Study Objectives**

### ***C1 Primary Aim***

The primary aim of this study is to establish feasibility of Adapted LiFE and a RCT design.

WE hypothesis that the feasibility pilot study will have high reach (60% recruitment and 80% retention rate of targeted participants), acceptance (80% of participants rating high satisfaction with Adapted LiFE), adherence (80% of all exercise activities achieved during the intervention period for each participant), fidelity (90% consistency of elements delivered by occupational therapists throughout the study period), safety (no adverse events caused by Adapted LiFE), and appropriate efficacy measurement selection (70% of the participants do not show floor/ceiling effects among balance, muscle strength, and habit outcomes at pre- and/or post-tests).

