## **2.g Data Collection and Follow-up for Withdrawn Subjects**

Data is directly entered into a REDCap database. REDCap servers are securely housed in an onsite, limited-access data center managed by the Division of Biostatistics at Washington University. All Web-based information transmission is encrypted. All data are stored on a private, firewall protected network. All users are given individual user IDs and passwords, and their access is restricted on a role-specific basis. REDCap was developed specifically around Health Insurance Portability and Accountability Act security guidelines and is implemented and maintained according to Washington University guidelines. Study data will be collected via tablet in the field and managed using REDCap electronic data-capture tools hosted at Washington University. REDCap is a secure, Web-based application designed to support data capture for research studies. If a participant is withdrawn from the study, his/her information will be kept in REDCap securely until the study is completed.

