### **1.i Data Collection Procedures for Adverse Events**

Adverse events will be recorded in rater/interventionist log within the same day of the visit or phone call. [name] and [name] will discuss if the participants need to be withdraw when an adverse event occur within 2 days.

Should there be a serious adverse event that occurs that increases the risks to the participants, the study will be stopped, an investigation will be conducted, and a findings report will be generated before the study is resumed(see 5.d).

Data of the withdrawn subjects other than reasons of withdrawal and demographic information will be deleted and excluded from data analysis.

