## ***F2 Study Outcome Measurements***

Feasibility outcomes include reach, acceptance, adherence, fidelity, safety, and appropriate efficacy outcome selection are described below. Feasibility outcomes will be assessed by the visit-by-visit grid, rater/interventionist log, the LiFE activity planner, and the feasibility questionnaire.

Reach is defined by recruitment and retention rate. Recruitment rate will be measured by the percentage of residents successfully enrolled in the study. Retention rate will be defined by the percentage of enrolled participants who complete the program. Reach will be documented by OT interventionists in interventionist logs and visit-by-visit grids in REDCap.

Acceptance will be surveyed by the feasibility questionnaire at the last session. The questionnaire contains a question, “Are you satisfied with the Adapted LiFE program?,” using a seven-point Likert scale from one (very unsatisfied) to seven (very satisfied). Follow-up questions will be asked to explore what makes the program satisfying or unsatisfying to the participant.

Adherence will be defined as the average percentage of exercise activities achieved during the intervention period that are recorded in the Adapted LiFE activity planner.

Fidelity will be assessed as the delivery of active and essential ingredients of the program as recorded by OT interventionists in visit-by-visit grids in REDCap. OT interventionists will meet weekly with the principle investigator to review the delivery of essential and active ingredients of Adapted LiFE for quality assurance.

Safety of the program will be evaluated by the number of adverse events documented throughout the study duration. This will be documented by OT interventionists in interventionist logs and visit-by-visit grids in REDCap.

---

The visit-by-visit grid is a checklist of all the elements that the interventionist should cover during each session. The interventionist will fill out the grid after every session is completed.

The rater/interventionist log is a survey that each rater/interventionist need to fill out after each visit to document any adverse event or special notes from a participant.

The LiFE activity planner is a weekly calendar for participants to fill out during the intervention sessions. Participants will record and check off the activities that they have completed.

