## **G4 Missing Outcome Data**

For feasibility outcomes, all data will be used in the final data analysis. Participants who have missing data will still be included.

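### The deletion rule in F 1.i conflicts with 2.g and G4 and can take a withdrawn participant's adverse events out of the F2 safety count; no contact after withdrawal is set

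*Combined protocol and SAP*

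**What the plan says.** All references are to the combined protocol and SAP.

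- **Withdrawal.** E2 2.f lets participants leave at any time and adds that they "will be withdrawn if there is a serious adverse event (SAE) that may impact participant's safety (see F5". F 1.i makes this a case decision and does not limit it to serious events: the responsible study staff "will discuss if the participants need to be withdraw when an adverse event occur within 2 days".
- **Storage.** E2 2.g: "If a participant is withdrawn from the study, his/her information will be kept in REDCap securely until the study is completed". Its heading announces follow-up of withdrawn subjects, but its text deals only with how data are held.
- **Deletion.** F 1.i: "Data of the withdrawn subjects other than reasons of withdrawal and demographic information will be deleted and excluded from data analysis".
- **Analysis.** G4: "For feasibility outcomes, all data will be used in the final data analysis". Participants with gaps in their data stay in.
- **Safety outcome.** F2: "Safety of the program will be evaluated by the number of adverse events documented throughout the study duration". On the source, F2 adds: "This will be documented by OT interventionists in interventionist logs and visit-by-visit grids in REDCap".
- **Safety criterion.** C1 lists, among the feasibility targets, "safety (no adverse events caused by Adapted LiFE".
- **Capture and reporting.** F 1.h wants every adverse event recorded, related or not. F 1.i places the recording on the day of a visit or call. F 1.k runs the reporting period from enrolment to the one-month call. F 1.j sends all serious events to the HRPO.

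**The concern.** The deletion sentence acts on the people in whom harm is most likely to be suspected. It spares two items, the reason for withdrawal and demographics, and adverse event records are neither of them. Those records are the ones from which F2 builds the safety outcome. If the sentence is followed, the count can only fall, so any bias runs toward finding the program safe.

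Safety is part of the primary feasibility aim, and its threshold is zero causal events. With 8 people in the Adapted LiFE group, a single record decides the result. There is a second, smaller gap. Events are captured at visits and calls, and the plan sets neither for someone who has been withdrawn, so how the triggering event ended may never be recorded.

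**Working it through.** The plan states no event rate, power or alpha on this point, so there is no figure to reproduce. The check compares the rules and then traces one participant through them.

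**1. The rules side by side**

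| Section | Withdrawn participant's data | Adverse event records |
|---|---|---|
| 2.g | kept until the study is completed | not mentioned; covered by the general rule |
| 1.i | deleted and left out of analysis, except withdrawal reason and demographics | not exempted |
| G4 | all data used for feasibility outcomes | covered, since safety is a feasibility outcome |

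One could try to reconcile 2.g and 1.i by supposing that data are kept until completion and then deleted. That does not help, because 1.i also excludes the data from analysis, which G4 contradicts. One could read G4 as meaning all data that remain after deletion, but no text says so or says which rule prevails. An analyst could follow 1.i in good faith.

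**2. One participant traced through the rules**

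Suppose an Adapted LiFE participant has an adverse event caused by the program and is withdrawn, and that it is the only causal event in the group.

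- The event is entered in the interventionist log (1.i).
- After withdrawal, 1.i removes the log entry and leaves the withdrawal reason.
- F2 counts from logs and grids and does not list withdrawal reasons as a source.

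Result:

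- Records kept: count = 1, so the C1 criterion fails. As a proportion of the group, 1/8 = 12.5%.
- Records deleted: count = 0, so the criterion is met. With the participant removed, 0/(8 − 1) = 0/7 = 0%.

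C1 and F2 use a count, not a proportion, so the result that matters is 1 against 0. Any other adverse events of the same person, serious or not, are lost in the same way, and the withdrawal reason would not normally preserve them.

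**3. Contact after withdrawal**

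The nominal session weeks in F 1.c are 1, 2, 3, 4, 6, 8 and 12. The one-month call then falls at about 12 + 4 = week 16. It is nominal because booster timing is flexible.

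F 1.e gives both groups a call one month after the last session and does not exclude withdrawn participants. E1 times the same call from the post-test, which a withdrawn participant may not have. If 1.e applies, a participant whose last session was session 1 is called at about 1 + 4 = week 5, which is 16 − 5 = 11 weeks early. If the last session was session 6, the call is at about 8 + 4 = week 12, which is 4 weeks early. The stated purpose of the call is questions about the program, and what it records could itself be deleted under 1.i.

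**4. Frequency**

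The only attrition figures are in D1, and they disagree: 9 enrolled in one sentence, 11 in another, with 8 completing. Scaled to 16 participants they give 16 × 1/9 = 1.8 or 16 × 3/11 = 4.4. No reasons for loss are given. That pilot also took people from age 60 who could qualify by worry about falling alone, whereas this trial requires age 70 and two falls or one injurious fall. Neither figure bounds withdrawals for adverse events here, so none is used.

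**The case against.** The strongest reply is that a serious event which leads to withdrawal is hard to lose. It would normally be the withdrawal reason, which 1.i keeps. It goes to the HRPO under 1.j. If it raises the risk to participants, the study stops until an investigation and a findings report are complete. In a 16-person study under close investigator monitoring (1.g), nobody is likely to call the safety criterion met with such an event on file. Sections 2.g, G4 and 1.k all lean toward keeping and counting.

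Much of this stands, and it rules out three stronger readings that a reader might infer:

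- **The plan erases serious adverse events.** The documents do not support this. The triggering event would usually remain visible, and its loss from F2 is a possible result of conflicting rules, not a clear one.
- **The withdrawal rule in 2.f is itself wrong.** Taking someone out after a safety-relevant serious event, on a case decision, is an ordinary protective rule. The defect lies in what 1.i does afterwards.
- **All contact ends at withdrawal.** Section 1.e can be read to include withdrawn participants. The text is unclear rather than silent.

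The reply leaves four points unanswered. No text turns a retained withdrawal reason or an HRPO report into an F2 event. A withdrawal reason need not state causality or outcome, and C1 turns on causality. Non-serious events, which C1 also counts and which can lead to withdrawal under 1.i, have no HRPO route. The participant's other adverse events have no protection under 1.i.

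**Conclusion.** The point holds in this form. Section 1.i contradicts 2.g and G4, and it does not exempt the logs and grids that feed the F2 safety count. If it is followed, a withdrawn participant's adverse events can leave that count. One dropped causal event is enough to change the C1 safety result from failed to met.

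The size rests on two assumptions: that 1.i is applied as written, and that the dropped event is the only causal one in the Adapted LiFE group. The documents give no rate of serious events or withdrawals for this population, so the likelihood is not estimated. The missing contact after withdrawal is a further, smaller weakness. It leaves the outcome of the triggering event, and later events up to the end of the 1.k period, without a sure route into the data. The consent text is not in the documents reviewed, so any limits it places on keeping data cannot be checked.

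The plan should be changed because the conflict bears on a primary-aim criterion and is easy to remove.

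**What to change.** 1. **F 1.i.** Replace the deletion sentence. Data collected up to withdrawal, including all adverse event records, are kept for every withdrawn participant whatever the reason, subject to the consent terms, and are counted in the F2 safety outcome. This agrees with 2.g and G4. Restricting the change to serious events would leave the same gap for people withdrawn after non-serious events and for those who choose to leave.
2. **E2 2.f and 2.g.** State that withdrawal for an adverse event stops the intervention sessions. Unless the participant refuses contact, follow the triggering event by phone to resolution or to the nominal one-month call (about week 16), whichever comes first, and ask about adverse events at that call. A single late call would not be enough: for an event in week 2 it would come about 16 − 2 = 14 weeks afterwards.
3. **Editorial only.** Correct the references to F5 (in 2.f) and 5.d (in 1.i), which match no section.

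The cost is protocol wording, possibly consent wording, and one or a few phone calls per affected participant. The change adds no visits and does not alter the sample size.

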## **2.g Data Collection and Follow-up for Withdrawn Subjects**

Data is directly entered into a REDCap database. REDCap servers are securely housed in an onsite, limited-access data center managed by the Division of Biostatistics at Washington University. All Web-based information transmission is encrypted. All data are stored on a private, firewall protected network. All users are given individual user IDs and passwords, and their access is restricted on a role-specific basis. REDCap was developed specifically around Health Insurance Portability and Accountability Act security guidelines and is implemented and maintained according to Washington University guidelines. Study data will be collected via tablet in the field and managed using REDCap electronic data-capture tools hosted at Washington University. REDCap is a secure, Web-based application designed to support data capture for research studies. If a participant is withdrawn from the study, his/her information will be kept in REDCap securely until the study is completed.

## ***E3 Study Intervention***

The treatment group will receive Adapted LiFE, and the control group will receive equivalence attention and time with an flexibility intervention program from Go4life.

### **3.a Treatment: Adapted LiFE**

Adapted LiFE teaches older adults to embed balance and lower extremity exercise activities into daily routines. The objective of LiFE is to form a habit to complete balance and muscle strength activities daily to improve balance and lower extremity muscle strength. A short summary of Adapted LiFE is at Table 2.

Participants will learn 10 exercise principles and 19 activities to increase balance and muscle strength during a 12 week intervention period (Table 3). For balance training, the core principle is to continue to practice a challenging balance activity, manage it, and then progress to another more challenging activity. For muscle strength training, the core principles are to overload muscles by adding weight, increasing repetitions, and moving slower to make the muscles progressively work harder.

Adapted LiFE is an intervention that aims to enhance self-efficacy through goal setting and creating appropriate outcome expectations to enhance participants' ability to repeatedly perform a target health behavior, which, in this case, is to form and adhere to a habit of exercise. Therefore, OT interventionists will guide participants to review the user manual and use a self-monitoring calendar (Adapted LiFE calendar) to plan and implement planned training activities.

The dose (visits and time) of Adapted LiFE consists of five weekly sessions and two booster sessions, which will be delivered by the OT interventionist in 12 weeks. Each session will last 40-60 minutes. The two booster sessions will be scheduled based on the needs of participants. If a participant has not finished learning all the activities after the fifth session, one or both booster sessions will be used to teach and implement the remaining activities, which will be conducted in the same manner as previous sessions. If a participant has completed learning all the activities, the first booster session (the 6th session) will be conducted with at least a two-week break after the 5th session. The second booster session (the 7th session) will be conducted at least a four-week break

---

after the 6th session. A phone follow-up call will be made after one month of the last intervention session as a booster session for participants to ask questions. feasibility outcome such as enrollment status, fidelity of intervention delivery will be documented by rater/interventionist log throughout the study period.

### **3.b Control: Go4life**

Participants in the attention control group will receive a gentle exercise intervention that consists of flexibility activities. Materials are modified from the Go4Life program (an online material developed for general older adults by National Instituted of Aging).

Participants will learn 19 gentle stretching activities during a 12 week intervention period. The OT practitioner will teach participants to gently stretch neck, shoulder, upper arm, upper body, chest, back, foot, leg, and hip. The OT practitioner will not actively guide or request participants to set goals or record activities.

The dose (visits and time) of the attention control intervention is the same as Adapted LiFE, which consists of five weekly sessions and two booster sessions. Each session will last 40-60 minutes. Nineteen gentle flexibility activities from Go4Life will be taught to participants. The OT interventionist will deliver the Go4Life user manual to the participant during the first visit and serve as a consultant for participants to ask questions about the flexibility activities. The self-monitoring calendar will be removed because self-monitoring is an active ingredient of the treatment effect of Adapted LiFE. The OT interventionist will not actively guide or request participants to set goals or record activities. feasibility outcome such as enrollment status, fidelity of intervention delivery will be documented by rater/interventionist log throughout the study period.

### **3.c Subject Compliance Monitoring**

Subject compliance is regarded as one of the feasibility outcome “adherence “ in this study (see F2).

### **3.d Blinding**

Participants and OT interventionist will not be blinded to the purpose of testing Adapted LiFE, and will be informed at the consent visit.

Raters will be blinded from the study. At baseline, raters will be blinded by randomizing participants after pre-test. At post-test, a blinded rater will be assigned to conduct the assessments. At one-month phone follow-up: a blinded rater will conduct the follow-up questionnaires.

## **F Study Procedures**

### **1.a Screening for Eligibility**

The screening process is for confirming eligibility to enrollment. Potential participants will be screened by phone or in-person using a script by a trained interviewer (See appendix 1). All in person screenings will take place in the potential participant's apartment, or other private area (whichever the potential participant prefers for privacy and convenience). The trained interviewer will screen participants eligibility by asking participants' age, how many time the participant had falling in the past year in a screening log (appendix 2), and evaluate if participants had attention/memory impairments with the Short Blessed Test (appendix 3).

---

